8.3. Variables

The following sections describe the study exposures, outcomes, and covariates (including patient demographics, clinical characteristics, comorbidities, and concomitant medications).

8.3.1. Exposures

DOACs of interest will include apixaban, rivaroxaban, edoxaban, and dabigatran. Exposures will be defined by corresponding ATC codes: B01AF02; B01AF01; B01AF03; and B01AE07, respectively. Initiators of DOACs are defined as new users of DOACs with no record of prescription for any DOAC during 12 months before index date.

Only a single index date is allowed per patient; if a patient qualifies as a new user of an exposure group multiple times, the patient will enter the cohort on the first qualifying exposure date. Patients with exposure to more than one DOAC on the index date will be excluded. Duration of treatment is calculated from the provided days supplied/duration data field. Fields with 0 are assumed to be 1 day. A grace period of 30 days between refills and risk window of 30 days after the last refill is used to define persistence. The operationalized definition of exposure will be recorded in the STaRT RWE template and is available on request.

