8.2.2. Study Periods

The study observation period spans July 1, 2013 through December 31, 2020, consisting of a drug indexing, baseline and follow-up periods (Figure 8.1). The drug indexing period will be used to ascertain DOACs initiation (index date). Baseline period is defined as 12 months prior to and including the index date. The follow-up period will include all available time after study index date. Patients will be followed in an “intention to treat” (ITT) approach from their index date until the end of follow-up period or the occurrence of the following events, whichever occurs first:

- First occurrence of the study outcomes of interest
- Death
- End of patient data
- End of patient registration with GP.

In addition, patients meeting the selection criteria will be followed in an “as-treated” approach from their index date until the end of the study follow-up period or the occurrence of the following events, whichever occurs first:

- First occurrence of the study outcomes of interest.
- Death
- End of patient data.
- End of patient registration with GP.
- Termination of exposure, crossover of exposure group, or addition of another DOAC.

Termination of exposure in the as-treated analysis is defined as having a gap exceeding 30 days (grace period) between the end of a prescription, based on its start date and duration, and the start of the next prescription, or if no additional prescription occurs. The termination date is defined as the prescription end date plus a 30-day risk window.

Comparative Effectiveness and Safety of DOACs in Patients with AFib in the UK

[figure not shown]

Figure 8.1 Study Design Diagram

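### Reading a recorded duration of 0 as one day falsely ends as-treated exposure for continuing patients whose zero-coded script really lasts 32 days or more

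*Protocol*

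**What the plan says.** Protocol section 8.3.1 (Exposures) sets the source of duration: "Duration of treatment is calculated from the provided days supplied/duration data field". It then gives the rule for zeros: "Fields with 0 are assumed to be 1 day". On persistence it says: "A grace period of 30 days between refills and risk window of 30 days after the last refill is used to define persistence".

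Section 8.2.2 (Study Periods) turns this into censoring. "Termination of exposure in the as-treated analysis is defined as having a gap exceeding 30 days (grace period) between the end of a prescription" continues with "based on its start date and duration, and the start of the next prescription, or if no additional prescription occurs". The censoring date follows: "The termination date is defined as the prescription end date plus a 30-day risk window". The as-treated list of follow-up endpoints includes "Termination of exposure, crossover of exposure group, or addition of another DOAC"; the ITT list has no such item.

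Three other places bear on the point:
- Table 9.1 makes persistence on treatment a diagnostic to be met before the inferential phase, with a threshold to be set from the data.
- Section 9 rules out imputation of missing values. Its sensitivity analyses are a pandemic-related cut-off of the study period and a high-dimensional propensity score. Neither varies the duration rule.
- Section 8.3.1 allows one index date per patient, so a patient whose exposure has been terminated does not come back in.

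**The concern.** The drugs are taken long term for stroke prevention, so a script meant to last one day would be unusual. A 0 more plausibly means that the duration was not captured. That is a judgement, since the protocol does not define the value. One day is nearly the smallest number that could be assigned, so the error runs in one direction: the supply ends too early and the gap to the next script looks too long.

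One such record can end a patient's as-treated follow-up for good while prescribing continues. At stake are the as-treated person-time and events, and the persistence figure that informs both the diagnostic threshold and the decision whether special methods for censoring are needed.

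**Working it through.** **Inputs from the protocol.** Zero duration set to 1 day (8.3.1); grace period 30 days and risk window 30 days (8.3.1, 8.2.2); prescription end = start + duration (8.2.2). The protocol states no figure of its own to reproduce here.

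**Assumptions.** The patient refills every L days and each script truly lasts L days. L and the share f of zero-coded scripts are not given.

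**Step 1: one zero-coded script starting on day 0.** It ends on day 1, so the gap to the next script is L − 1. Exposure terminates if L − 1 > 30, that is, if L ≥ 32. The censoring date is 1 + 30 = day 31, counted from the start of that script.

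| Refill interval L (days) | Gap L − 1 | Result |
|---|---|---|
| 28 | 27 | continues |
| 30 | 29 | continues |
| 31 | 30 | continues |
| 32 | 31 | censored day 31 |
| 56 | 55 | censored day 31 |
| 84 | 83 | censored day 31 |

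If the start day counts as the first day of supply, the threshold moves to L ≥ 31 and the censoring date to day 30. The conclusion is the same.

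**Step 2: comparison with correct durations.** With L = 56 and the true duration recorded, the gap is 0. Twelve scripts are followed to 12 × 56 + 30 = day 702. With a 0 on the first script, follow-up stops on day 31. With a 0 only on the third script, which starts on day 112, it stops on day 112 + 31 = 143.

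**Step 3: a 0 on the last script.** Here the length of the script does not protect the patient: the end date falls L − 1 days too early. For twelve 28-day scripts, follow-up ends at 11 × 28 + 1 + 30 = day 339 instead of 12 × 28 + 30 = day 366, a loss of 27 days.

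**Step 4: how often, under assumptions.** With 56-day scripts there are about 365/56 ≈ 6.5 scripts a year. If zeros are independent across scripts, the probability that a continuing patient has at least one is 1 − (1 − f)^(6.5 × years). The second horizon, 2.3 years, is the median follow-up in Table 9.1.

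| f (assumed) | 1 year | 2.3 years |
|---|---|---|
| near 0 | near 0% | near 0% |
| 2% | 1 − 0.98^6.5 = 12.3% | 1 − 0.98^14.95 = 26.1% |
| 5% | 1 − 0.95^6.5 = 28.4% | 1 − 0.95^14.95 = 53.6% |

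Counting only the six whole scripts in a year gives 11.4% and 26.5% in place of 12.3% and 28.4%. For intervals up to 31 days the false stop does not occur; only the loss in Step 3 remains.

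**The case against.** **The premise is not in the document.** The protocol does not say that a 0 is an unrecorded duration, nor how common zeros are. Section 9 reports that exposure groups were explored before the protocol was written, so zeros may already be known to be rare. This stands: the size is open, and zero effect is within the range. It does not make one day a plausible value for a zero.

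**The percentages rest on assumed inputs.** They do. If zeros cluster within patients or practices, fewer patients are affected than under independence.

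**The hazard ratio need not be biased.** A reader might infer that a different frequency of zeros by drug, for example between products with different dosing frequencies, would by itself bias the as-treated hazard ratio. The documents do not support that. No frequency of zeros by drug is given. Moreover, censoring that differs by arm for clerical reasons, but is unrelated to prognosis within arm, is independent censoring: a Cox model then loses person-time and precision. Bias requires zeros to be related to prognosis, or a hazard ratio that changes over time. Likewise, events and time before a false stop are validly counted; what is lost is what comes after.

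**Safeguards exist.** Table 9.1 promises appropriate methods if censoring is substantial. Section 11 requires variables to be tabulated and outliers examined, and allows definitions to be changed by amendment. These could reveal the problem, but none replaces the one-day rule, asks for zeros by drug, or separates a clerical stop from a real one.

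**Replacing zeros conflicts with the no-imputation statement.** Setting 0 to 1 already assigns a value. The conflict is settled by stating an exception.

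**Conclusion.** The point holds as a defect in a stated rule with limited reach. Under sections 8.3.1 and 8.2.2 together, a continuing patient whose zero-coded script really lasts 32 days or more is terminated 31 days after that script starts. Persistence is understated, and later as-treated person-time and events are discarded. No planned sensitivity analysis tests the rule.

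Two further readings go too far. The stop is not day 31 of follow-up for everyone; that is so only when the index script carries the 0. The study's results as a whole are not in doubt either: ITT follow-up does not use duration, and the effect is confined to the as-treated analysis and the persistence diagnostic.

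The size cannot be determined from the protocol. For 56-day scripts and independent zeros it ranges from near 0% to about 12% (2% zeros) or 28% (5% zeros) of continuing patients falsely stopped within a year. The change is worth making because the rule errs in one direction and is cheap to replace.

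**What to change.** In section 8.3.1, replace the one-day rule as follows:
1. Where quantity and daily units are held in the extract (the protocol does not show whether they are), set a zero duration to quantity divided by daily units.
2. Otherwise use the patient's previous non-zero duration or the product-specific median non-zero duration.
3. In section 9, state this as an explicit exception to the no-imputation rule.
4. In the diagnostic phase, before outcomes by exposure are viewed, tabulate the share of zero durations by drug.
5. Keep the one-day rule as a sensitivity analysis for the as-treated results and the persistence diagnostic.

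The cost is a small recode of the exposure measure, an added table and a documented amendment, which section 11 already provides for. The downside is some error in the imputed durations: where the assigned value is too long, a real discontinuation is recognised late. The comparison with the one-day rule shows how much the choice matters.

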8.3.1.1. Primary Exposure Groups

- *Exposure Group 1:* Initiators of apixaban
- *Exposure Group 2:* Initiators of rivaroxaban

Comparative Effectiveness and Safety of DOACs in Patients with AFib in the UK

8.3.1.2. Secondary Exposure Groups

The following independent Exposure Groups will be created:

- *Exposure Group 3*: Initiators of edoxaban
- *Exposure Group 4*: Initiators of dabigatran
- *Exposure Group 5*: Initiators of rivaroxaban, edoxaban, and dabigatran
- *Exposure Group 6*: Initiators of apixaban, edoxaban, and dabigatran
- *Exposure Group 7*: Initiators of apixaban, rivaroxaban, and dabigatran
- *Exposure Group 8*: Initiators of apixaban, rivaroxaban, and edoxaban

8.3.1.3. Primary Comparison

- *Primary Comparison*: initiators of apixaban vs initiators of rivaroxaban (i.e., *Exposure Group 1 vs Exposure Group 2*)

8.3.1.4. Secondary Comparisons

- *Secondary Comparison 1*: initiators of apixaban vs initiators of edoxaban (i.e., *Exposure Group 1 vs Exposure Group 3*)
- *Secondary Comparison 2*: initiators of apixaban vs initiators of dabigatran (i.e., *Exposure Group 1 vs Exposure Group 4*)
- *Secondary Comparison 3*: initiators of apixaban vs initiators of other DOACs class (i.e., *Exposure Group 1 vs Exposure Group 5*)
- *Secondary Comparison 4*: initiators of rivaroxaban vs initiators of edoxaban (i.e., *Exposure Group 2 vs Exposure Group 3*)
- *Secondary Comparison 5*: initiators of rivaroxaban vs initiators of dabigatran (i.e., *Exposure Group 2 vs Exposure Group 4*)
- *Secondary Comparison 6*: initiators of rivaroxaban vs initiators of other DOACs class (i.e., *Exposure Group 2 vs Exposure Group 6*)
-
- *Secondary Comparison 7*: Initiators of edoxaban vs initiators of other DOACs class (i.e., *Exposure Group 3 vs Exposure Group 7*)
- *Secondary Comparison 8*: initiators of dabigatran vs initiators of other DOACs class (i.e., *Exposure Group 4 vs Exposure Group 8*)

8.3.2. Outcomes

The primary outcome is ischemic or hemorrhagic stroke. Secondary outcomes include the occurrence of all-cause mortality, myocardial infarction, transient ischemic attacks, major bleeding events, and major adverse cardiovascular events (MACE). Major bleeding is defined as a composite outcome of major intracranial (including hemorrhagic stroke), gastrointestinal, and urogenital bleeds. MACE outcomes will be a composite endpoint of angina, myocardial infarction, and stroke.

Outcomes of interest will be measured during the study follow-up period, and defined by corresponding Read Medical Codes and ICD-10 diagnosis codes at the primary care setting. The operational definitions of each outcome will be recorded in the STaRT-RWE template and are available on request.

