In each comparison cohort, multivariable logistic regression will be used to estimate the probability of a patient's initiation of the exposure given baseline covariates and cohort entry year (i.e., the propensity score). Propensity score matching between exposure groups will be performed using 1:1 nearest neighbor matching without replacement with a maximum matching caliper of 0.01. In addition to graphical depictions of propensity score distributions, the absolute standardized differences (ASD) in proportions and means of baseline characteristics will be estimated to examine comparability of exposure groups. Covariates with $ASD \leq 0.10$ are considered balanced between comparator groups.³³ Covariates with small imbalances $0.10 \leq ASD \leq 0.15$ may be deemed balanced if the covariate does not predict the outcome among the referent group.

Cox proportional hazards regression (outcomes model) will be used to estimate hazard ratios (HR) and 95% CI for each outcome after propensity score matching. The incidence of stroke and secondary outcomes will be compared between individual DOACs in primary and secondary comparisons as mutually exclusive cohorts.

Subgroup analyses that will be considered include DOACs initiators with prior warfarin use; age (<75 and ≥ 75 years); concomitant aspirin use; CHA₂DS₂ VASc score (0-1, 2-3, and ≥ 4), and selected comorbid conditions, e.g. diabetes, heart failure, and BMI status (<30 and ≥ 30 kg/m²).

Sensitivity analyses will be performed to assess the impact of varying the study period on study findings by limiting analyses on data up to February 28, 2020 to account for potential impact of COVID-19 pandemic on healthcare utilization.

Additionally, high-dimensional propensity score (HdPS) analysis will be used as a sensitivity analysis to estimate the association between treatment with DOACs and the primary outcome of stroke. The HdPS approach is a 7-step algorithm that empirically identifies a pool of covariates from different data dimensions based on their prevalence, and then selects a subset of the covariates for inclusion in a propensity score model based on their potential to bias the exposure-outcome association.³⁰

Missing values will be reported as missing, and no imputation will be undertaken. All data analysis will be conducted using Aetion Evidence Platform® (2021), software for real-world data analysis. Aetion, Inc. <https://www.aetion.com>.

10. Limitations of the Research Methods

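### MACE includes coded angina but no death component, so a fatal MI or stroke recorded only as a death is censored as a non-event; report a death-inclusive composite beside it

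*Protocol*

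**What the plan says.** Four statements in the protocol matter when read together.

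- **Composite.** Section 8.3.2: "MACE outcomes will be a composite endpoint of angina, myocardial infarction, and stroke". Death is not a component, whether cardiovascular or from any cause.
- **Other secondary outcomes.** Section 8.3.2: "Secondary outcomes include the occurrence of all-cause mortality, myocardial infarction, transient ischemic attacks, major bleeding events, and major adverse cardiovascular events (MACE"). All-cause mortality is analysed on its own. Neither cardiovascular death nor angina alone is listed.
- **Ascertainment.** Section 8.3.2 has outcomes "defined by corresponding Read Medical Codes and ICD-10 diagnosis codes at the primary care setting". Section 13 restricts the study to structured fields and rules out chart review. The code lists sit in the STaRT-RWE template, which is not part of the protocol.
- **Follow-up and model.** Section 8.2.2 follows patients "from their index date until the end of follow-up period or the occurrence of the following events, whichever occurs first"; the list that follows includes death, in both the ITT and the as-treated analysis. Section 9: "Cox proportional hazards regression (outcomes model) will be used to estimate hazard ratios (HR) and 95% CI for each outcome after propensity score matching".

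Section 10 discusses misclassification when a diagnosis code is present without true disease. It does not discuss the reverse case, a true fatal event that never receives a code.

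**The concern.** Sudden fatal MI and fatal stroke are among the most severe events that MACE and the stroke outcome are meant to count. They are also the events most easily missed by a definition that needs a diagnosis code, because the patient may die before one is entered. Under the stated rules such a patient contributes person-time up to death and then leaves as a non-case.

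Censoring at death in a Cox model is not wrong in itself: it estimates the hazard of a coded event among those still alive. The difficulty is that here the death may itself be the event of interest. A competing-risk model that treats the death as a different event would not recover it.

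Two things are at stake. Table 9.1 says that NICE would typically feed effect estimates into economic models and can allow for quantified uncertainty, but the confidence interval does not reflect events missing from the definition. And since angina is not reported alone, a reader cannot see how much of MACE is angina and how much is MI or stroke.

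**Working it through.** The protocol gives no event rate, event count or power for MACE, so there is no stated figure to reproduce. The check is a reading of the rules, followed by illustrations whose inputs are labelled.

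**Step 1. Follow one patient through the rules.** A new user with no prior stroke, MI or angina (section 8.2.1.2 excludes them) has a fatal MI, and the practice records only the death.

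- MACE, MI: no diagnosis code, so censored at the date of death.
- All-cause mortality: counted as an event.

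A fatal stroke runs the same way for MACE and for the primary outcome. If the practice does code the MI or stroke, for example from hospital information (section 7), the event is counted.

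**Step 2. When the HR is biased.** Let f0 and f1 be the shares of true first events seen only as a death in the comparator and index groups. Then

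coded HR = true HR × (1 − f1) / (1 − f0).

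If f1 = f0, the coded HR equals the true HR. That is the same as saying that the drug effect is equal on coded and on death-only events. Bias needs f1 ≠ f0.

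**Step 3. Size if the effects differ (assumed inputs).** With f the comparator-group share that is death-only,

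true HR ≈ (1 − f) × HR_coded + f × HR_fatal.

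Assume HR_coded = 1.00, which is what the report would show.

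| f (assumed) | HR_fatal 0.7 | HR_fatal 1.0 | HR_fatal 1.3 |
|---|---|---|---|
| 10% | 0.90 + 0.07 = 0.97 | 1.00 | 0.90 + 0.13 = 1.03 |
| 20% | 0.80 + 0.14 = 0.94 | 1.00 | 0.80 + 0.26 = 1.06 |
| 30% | 0.70 + 0.21 = 0.91 | 1.00 | 0.70 + 0.39 = 1.09 |

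The middle column is the null case: no bias, whatever the share lost.

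**Step 4. Precision if the loss is equal in both groups.** Table 9.1 gives planning inputs for stroke only: HR 0.80, one-sided 0.05, 80% power, 1:1. Schoenfeld's formula gives

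d = 4 × (1.645 + 0.842)² / (ln 0.80)² ≈ 497 events.

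If there are 497 true events and 10-30% are lost, 447-348 remain. Power = Φ(√(d/4) × |ln 0.80| − 1.645) falls from 80% to 76%-67%. The protocol states no event count, so this shows scale only.

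**Step 5. Why angina should be visible separately (assumed inputs).** If the HR is 0.80 for MI or stroke and 1.00 for angina, the same weighting gives:

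- angina share 20%: 0.8 × 0.80 + 0.2 × 1.00 = 0.84
- angina share 50%: 0.5 × 0.80 + 0.5 × 1.00 = 0.90

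**Step 6. What adding all-cause death does (assumed inputs).** Suppose the true stroke HR is 0.80 and deaths unrelated to treatment (HR 1.00) make up part of stroke-or-death:

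- 50% of events: 0.5 × 0.80 + 0.5 × 1.00 = 0.90
- 80% of events: 0.2 × 0.80 + 0.8 × 1.00 = 0.96

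This shift of 0.10-0.16 is larger than the 0.03-0.09 in Step 3, which argues against replacing the present endpoints.

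**The case against.** The strongest reply is that this is a choice of endpoint, openly stated, with no contradiction or wrong figure. MACE is defined without ambiguity, and prior angina is excluded, so the angina component is incident disease. Section 10 says the outcomes are in the QOF, which rewards coding, and that validated algorithms will be used. Section 7 says GPs hold information from hospitalisations, so many in-hospital deaths after MI or stroke may carry a code. The unseen code lists may include fatal-event codes. All-cause mortality has its own rates and HRs, so a material excess of deaths on one drug would show next to MACE. An extra sensitivity analysis is often left to a statistical analysis plan, which was not available here.

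Most of this stands. It means that the size of the loss cannot be stated, that nothing supports calling angina an invalid component, and that the absence of a particular sensitivity analysis is not a fault in itself. What it does not answer is the rule: a death-only fatal MI or stroke is censored under the text as written. The separate mortality HR cannot be added to the MACE HR afterwards, because patients with both a coded event and a later death would count twice. A first-event analysis is needed.

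Two stronger readings are tempting, and the documents support neither. The first is that a drug with more fatal events will look better. In Step 3 it looks equal, at 1.00. To look better it would need a lower coded-event rate: equal total rates with 30% death-only on one drug and 20% on the other would give 0.70 / 0.80 = 0.875. Nothing in the protocol suggests such a difference. The second is that MACE should be redefined with all-cause death in place of angina. Step 6 shows why that is a debatable trade and not a correction.

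**Conclusion.** The point holds as a low-priority, cheap improvement. As written, fatal MI and stroke recorded only as deaths are censored as non-events in MACE, in MI and in the primary stroke outcome, and MACE counts angina without showing its share.

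The size is not known. The 10-30% death-only share and the fatal HRs of 0.7 and 1.3 are assumptions with no anchor in the protocol; under them the true HR lies between 0.91 and 1.09 when 1.00 is reported. If the loss is proportional in both groups, the HR is unbiased and only events and precision are lost. The conclusion also assumes that the STaRT-RWE definitions do not already capture these deaths as MI or stroke.

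**What to change.** Keep the present MACE definition and the primary stroke outcome. Add to section 8.3.2 or section 9, or to the statistical analysis plan if there is one:

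1. A supplementary first-event composite of MI, stroke or all-cause death, reported beside MACE for the same comparisons, with angina shown as a separate component.
2. For apixaban versus rivaroxaban, a sensitivity analysis of stroke or all-cause death.

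Report first events by type and drug. The number of deaths that come first, without a coded MI or stroke, gives an upper bound on the fatal MI and stroke events that could have been lost in each group.

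Specify both before the inferential phase, while section 9 still keeps outcomes by exposure unseen, and record them as an amendment as section 11 requires.

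**Cost.** A few lines of text and extra Cox models on data already held. Deaths are already needed for censoring and for the mortality outcome, so no linkage is required. The downside is that all-cause death brings in non-cardiovascular deaths and pulls the composite HR towards the mortality HR, so these analyses should be labelled as supplements and read together with the existing endpoints.
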